5.3 Treatment assignment and randomization

At Baseline, all eligible patients will be randomized via Interactive Response Technology (IRT) to 1 of the 2 treatment arms described in Section 5.2. The investigator or his/her delegate will contact the IRT after confirming that the patient fulfills all the inclusion/exclusion criteria. The IRT will assign a randomization number to the patient, which will be used to link the patient to a treatment arm and will specify a unique medication number for the first package of study treatment to be dispensed to the patient. The randomization number will not be communicated to the caller.

The randomization numbers will be generated using the following procedure to ensure that treatment assignment is unbiased and concealed from patients and investigator staff. A patient randomization list will be produced by the IRT provider using a validated system that automates the random assignment of patient numbers to randomization numbers. These randomization numbers are linked to the different treatment arms, which in turn are linked to medication numbers. A separate medication list will be produced by or under the responsibility of Novartis Drug Supply Management using a validated system that automates the random assignment of medication numbers to packs containing the study drug(s).

Patients will be stratified at randomization on the basis of PsA or axSpA disease. Based on enrollment target, it is planned that approximately 50% of randomized patients should be PsA

and approximately 50% axSpA patients to ensure a balanced patient population for the assessment of efficacy and safety.

Additionally, it is planned to enroll no more than 40% TNF-IR patients in the study.

The randomization scheme for patients will be reviewed and approved by a member of the Integrated Quantitative Sciences Randomization Group.

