9.4.2 Statistical model, hypothesis, and method of analysis

The null hypothesis to be rejected is that the odds of response Week 24 are equal in both treatment groups. The corresponding alternative hypothesis is that the odds of response at Week 24 are higher under secukinumab compared to placebo.

Let pj denote the proportion of responders at Week 24 for treatment group j, j=0, 1, where

- 0 corresponds to placebo
- 1 corresponds to secukinumab

The following hypotheses will be tested:

H0: (p1 / (1 - p1)) / (p0 / (1 - p0)) = 1 versus HA: $(p1 / (1 - p1)) / (p0 / (1 - p0)) \neq 1$

In other words:

HA: The odds ratio of achieving a response at Week 24 for secukinumab vs Placebo is different from 1.

The primary analysis will be performed comparing treatments with respect to the primary efficacy variable in a logistic regression model with the factors treatment, $TNF\alpha$ inhibitor status and stratification factor diagnosis (PsA or axSpA). The odds ratio and its 95% confidence interval and p-value will be given.

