9.5 Analysis of secondary variables

9.5.1 Efficacy variables

9.5.1.1 Heel pain

The mean change from Baseline of heel pain at 24 weeks, measured on a 10-point NRS will be analyzed using an Analysis of covariance (ANCOVA)-model with factors treatment, country and diagnosis (PsA or axSpA) and with covariate baseline heel pain. The adjusted (LS-) mean difference will be calculated as a point estimate together with its corresponding 95% confidence interval and p-value.

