### 2.5.2 Statistical hypothesis, model, and method of analysis

The null hypothesis to be rejected is that the odds of response Week 24 are equal in both treatment groups. The corresponding alternative hypothesis is that the odds of response at Week 24 are higher under secukinumab compared to placebo.

In other words: Let  $p_j$  denote the proportion of responders at Week 24 for treatment group  $j$ ,  $j=0, 1$ , where

- 0 corresponds to placebo
- 1 corresponds to secukinumab

The following hypotheses will be tested:

$H_0: (p_1 / (1-p_1)) / (p_0 / (1-p_0)) = 1$  versus  $H_1: (p_1 / (1-p_1)) / (p_0 / (1-p_0)) \neq 1$

In other words,  $H_1$ : The odds ratio of achieving a response at Week 24 for secukinumab vs Placebo is different from 1.

The hypotheses can also be re-written as a difference of proportions as follows:

In statistical terms,  $H_0: p_1 = p_0$ ,  $H_1: p_1 \neq p_0$ , i.e.

$H_1$ : The difference of proportions at Week 24 for secukinumab vs Placebo is different from 0.

The primary analysis will be performed comparing treatments with respect to the primary efficacy variable in a logistic regression model with the factors treatment, country and

[figure not shown]
stratification factor diagnosis (PsA or axSpA). The odds ratio and its 95% confidence interval (CI) and p-value will be presented comparing secukinumab to placebo at Week 24.

The study is said to be positive/declared as success if the lower limit of 95% CI of odds ratio is greater than 1.

The primary endpoint (percentage of patients with resolution of Achilles tendon enthesitis) will additionally be analyzed separately for the subgroups of patients with PsA or axSpA, using the same model as for the respective pooled, overall population tests (except for the stratification factor). Those two subgroup analyses are included in the confirmatory testing strategy. The primary model will also be recalculated with the stratification factor included as well as with respective term for a strata\*treatment interaction.

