## **Analysis of secondary efficacy variables**

- Heel pain**

The mean change from Baseline of heel pain at 24 weeks, measured on a 10-point NRS will be analyzed using an Analysis of covariance (ANCOVA) model with factors treatment, country and diagnosis (PsA or axSpA) and with covariate baseline measurement of heel pain. The adjusted (LS) mean difference will be calculated as a point estimate together with its corresponding 95% confidence interval and p-value.

- Bone marrow oedema (PsAMRIS)**

The percentage of patients with an improvement of bone marrow oedema will be analyzed using a logistic regression model with factors treatment, country and diagnosis (PsA or axSpA). The odds ratio and its 95% confidence interval (CI) and p-value will be presented comparing secukinumab to placebo at Week 24.

- Enthesitis Assessment (LEI)**

The 4-site LEI (i.e. score with the four correct sites: lateral epicondyle humerus L + R and proximal achilles L + R) will be analyzed using a logistic regression model with factors treatment, country and diagnosis (PsA or axSpA). The odds ratio and its 95% confidence interval (CI) and p-value will be presented comparing secukinumab to placebo at Week 24.

- Physician's global assessment of disease activity**

Physician's assessment, measured on a VAS scale will be analyzed using an ANCOVA model with factors treatment, country and diagnosis (PsA or axSpA) and with covariate baseline value of global assessment of disease activity. The adjusted (LS-) mean difference will be calculated as a point estimate together with its corresponding 95% confidence interval and p-value.

- Physician's global assessment of heel enthesiopathy activity**

Physician's assessment, measured on a VAS scale will be analyzed using an ANCOVA model with factors treatment, country and diagnosis (PsA or axSpA) and with covariate baseline measurement of the global assessment of heel enthesiopathy. The adjusted (LS-) mean difference will be calculated as a point estimate together with its corresponding 95% confidence interval and p-value.

- Patient's global assessment of disease and heel enthesiopathy activity**

Refer to section 2.11 for analyses details.

- SF-36 or SF-36v2**

Refer to section 2.11 for analyses details

The time courses of secondary endpoints (percentage of patients with resolution of enthesitis as assessed by LEI, mean change from baseline for heel pain in NRS, Physician's / patient's

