### 2.11 Patient-reported outcomes

#### Patient's global assessment of disease activity

Patient's global assessment of disease activity, measured on a VAS scale will be analyzed using an ANCOVA model with factors treatment, country and diagnosis (PsA or axSpA) and

with covariate baseline measurement of the global assessment of disease activity. The adjusted (LS-) mean difference will be calculated as a point estimate together with its corresponding 95% confidence interval and p-value.

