#### **5.4.3 Secondary analysis**

Categorical variables will be analyses using the logistic model, code is described above.

Endpoints with continuous data type expected to be normally distributed will be analyzed using an analysis of covariance (ANCOVA) model with treatment and baseline stratification factor, country and baseline value as covariate. Confidence intervals for the difference between each dose of secukinumab and placebo will be calculated.

SAS code for ANCOVA:

```
proc mixed data=aaa;  
class TRT COUNTRY STRATA;  
model response = TRT STRATA COUNTRY BASE / s;  
lsmeans TRT / diff;  
run;
```

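### The ANCOVA for the six continuous secondary endpoints omits TNFα-inhibitor status, which the protocol's primary model includes: a modest efficiency and consistency point

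*SAP*

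**What the plan says.** **ANCOVA, SAP.** The heel pain model in SAP 2.7.2 is a "model with factors treatment, country and diagnosis (PsA or axSpA) and with covariate baseline measurement of heel pain". The two physician's global assessments (2.7.2), the two patient's global assessments and SF-36 (2.11) have the same structure, each with its own baseline value. The code in 5.4.3 is "model response = TRT STRATA COUNTRY BASE / s". That makes six comparisons, none with a TNF term.

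**ANCOVA, protocol.** Section 9.5.1.1 fits heel pain "with factors treatment, country and diagnosis (PsA or axSpA) and with covariate baseline heel pain". Sections 9.5.1.3 and 9.5.1.4 carry that model over to the global assessments and SF-36. On these endpoints the two documents agree.

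**Primary model.** Protocol 9.4.2 uses treatment, TNFα "inhibitor status and stratification factor diagnosis (PsA or axSpA"). By analogy, protocol 9.5.1.2 applies the same model to bone marrow oedema. SAP 2.5.2 instead analyses the primary "efficacy variable in a logistic regression model with the factors treatment, country and" diagnosis, with no TNF term, while SAP section 4 records no change to protocol-specified analyses.

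**Population and randomization.** Protocol 5.3 stratifies on diagnosis only and states: "Additionally, it is planned to enroll no more than 40% TNF-IR patients in the study". Previous PsA/axSpA therapies are recorded at screening (protocol Table 6-1).

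**Status of the endpoints.** Protocol 9.5.1.7 and SAP 2.7.2 place all secondary endpoints outside the confirmatory framework. SAP section 3 gives no sample size justification for them.

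**The concern.** The protocol judges TNFα-inhibitor status worth adjusting for in its primary analysis, and lists it for subgroup and effect-modification analyses (9.4.4, 9.5.1.6). Neither document says why the continuous endpoints are treated differently. Because the factor is not a stratum, the arms can differ in their share of TNF-exposed patients by chance.

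If exposed patients improve less after allowance for baseline, diagnosis and country, two things follow. Their shortfall stays in the residual variance and widens the interval for each of the six comparisons. Any imbalance that happens to occur also remains in the point estimate of this one trial. At stake is a little precision on supportive endpoints, and a consistent covariate set across the plan. Once the sponsor is unblinded after the Week 24 lock, adding the covariate would look data-driven.

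**Working it through.** **The plan's own figure.** There is none to reproduce on this point: the documents give no sample size, SD or power for any ANCOVA endpoint.

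**Inputs from the documents.** 100 patients per arm, 1:1 (protocol 9.8). TNF-IR share capped at 40% (protocol 5.3). Inclusion criterion 16 requires TNF-exposed patients to have had an inadequate response or intolerance, and the glossary counts intolerance as inadequate response, so the cap is a fair upper guide to the exposed share.

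**Assumptions, not in the documents.** Exposed share p = 0.20 to 0.40. Exposed patients improve d = 0.3 to 0.5 less, in units of the residual SD of the model that includes TNF status.

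**Formulas.**
- Variance inflation when the term is omitted: 1 + p(1−p)d². SE inflation is its square root minus 1.
- Extra patients needed to offset it: 200·p(1−p)d².
- SD of the between-arm difference in exposed share: √(2p(1−p)/100). The 95% limit is 1.96 times this.
- Shift of the estimate at that limit: limit × d.

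| p | d | p(1−p)d² | SE inflation | Patients of 200 | 95% imbalance (points) | Shift (SD) | Power if 80.0% with the term |
|---|---|---|---|---|---|---|---|
| 0.20 | 0.3 | 0.0144 | 0.7% | 2.9 | ±11.1 | 0.033 | 79.4% |
| 0.20 | 0.5 | 0.0400 | 2.0% | 8.0 | ±11.1 | 0.055 | 78.4% |
| 0.40 | 0.3 | 0.0216 | 1.1% | 4.3 | ±13.6 | 0.041 | 79.2% |
| 0.40 | 0.5 | 0.0600 | 3.0% | 12.0 | ±13.6 | 0.068 | 77.7% |

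Outside that range, at p = 0.40: d = 0 costs nothing, d = 0.2 inflates the SE by 0.5%, and d = 0.8 inflates it by 7.4% (power 74.2%).

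**Scale of the shift.** The treatment SE is √(2/100) = 0.141 SD, so the largest shift in the table is 0.068/0.141 = 0.48 of one SE. With an assumed residual SD of 25 mm on a 100-mm VAS, shifts of 0.033 to 0.068 SD are about 0.8 to 1.7 mm.

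**Validity check.** A simulation with no treatment effect used 4,000 runs per scenario, 100 per arm and p = 0.40, with stratum and baseline in the model and country left out. The mean treatment estimate was within 0.002 of zero with and without the TNF term.

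| d | Type I error without the term | Type I error with the term |
|---|---|---|
| 0 | 4.6% | 4.6% |
| 0.5 | 4.3% | 4.4% |
| 0.8 | 5.6% | 5.2% |

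The simulation SE is √(0.05×0.95/4000) = 0.34 points, so all six rates lie within about two simulation SEs of 5%.

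**The case against.** The strongest reply is that this is a valid pre-specified model. Both documents give the same ANCOVA, and it contains the only stratification factor and the baseline value of each outcome. Leaving out an unstratified covariate breaks no rule, and no confirmatory decision or power claim depends on these endpoints. The protocol never calls TNF status prognostic; that is an inference from its place in the primary model. All of this stands, and it limits the point to an inexpensive improvement.

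It does not remove the point. The unexplained difference in covariates remains, and SAP Table 1.2-1 still frames these endpoints as demonstrating superiority, each with an adjusted difference, interval and p-value.

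The documents do not support some stronger readings that a reader might infer:

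- **That the estimates are biased.** Chance imbalance is not bias. Randomization keeps the estimator unbiased, and the ANCOVA interval already reflects this variation.
- **That precision is certainly lost.** That depends on a prognostic effect which the documents do not give.
- **That up to 40% of patients are imbalanced.** The 40% is a cap on the TNF-IR share. It says nothing about the difference between arms.
- **That the SAP's ANCOVA departs from the protocol's.** It follows it. The departure is in the primary model.
- **That the link between TNF exposure and syringe number in PsA (protocol 5.2) calls for this term.** Syringe number is matched between arms. The active dose differs, which is a matter of effect modification that a main-effect term does not address.

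**Conclusion.** The omission is real, covers all six continuous secondary comparisons and is in both documents. It is a modest efficiency and consistency point on exploratory endpoints. Under the assumed 20-40% exposed and 0.3-0.5 SD, the standard error is inflated by about 0.7-3%, and at most about 2 points of power are lost from 80%. With no prognostic effect the gain is zero.

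The weightier issue is the neighbouring one: the SAP's primary model has country where the protocol's has TNFα-inhibitor status. The SAP's deviation table also still codes prior TNF exposure as a deviation (INCL16, EXCL09). This suggests, as an inference, that the SAP was not updated for Amendment 3. Correcting the primary model alone would leave the ANCOVAs unchanged, so both should be handled together.

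**What to change.** Before the Week 24 database lock:

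1. Define TNFα-inhibitor status as naive / exposed, derived from the previous therapies recorded at screening.
2. Add it as a class factor to the ANCOVA text in protocol 9.5.1.1 (and so 9.5.1.3 and 9.5.1.4) and in SAP 2.7.2, 2.11 and 5.4.3. In the code, add TNF to the class statement and use `model response = TRT STRATA TNF COUNTRY BASE`.
3. In the same revision, reconcile the SAP's primary model (treatment, country, diagnosis) with the protocol's (treatment, TNFα-inhibitor status, diagnosis), and record any remaining difference in SAP section 4.

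The cost is one degree of freedom in about 200 patients, with no new data, plus a text change in each document. The protocol change goes through a written amendment under its section 11.1.

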#### **5.5 Rule of exclusion criteria of analysis sets**

##### **Table 5.1-4 Protocol deviations that cause subjects to be excluded**

Deviation ID	Description of Deviation	Exclusion in Analyses	Severity code
INCL01A	ICF is not signed or missing or date of signing ICF is missing	EXCLUDE FROM FAS AND SAF	3
INCL01B	ICF date is after visit or assessment date	INCLUDE IN EVERYTHING	0
INCL02A	Pregnant or lactating female patients	INCLUDE IN EVERYTHING	0
INCL02B	Age is less than 18 years	INCLUDE IN EVERYTHING	0
INCL03A	Diagnosis of PsA classified by CASPAR criteria with no symptoms or symptoms for less than 6 months	INCLUDE IN EVERYTHING	0
INCL03B	Active PsA as not assessed by greater than 1/78 tender joints and greater than 1/76 swollen joints at Baseline.	INCLUDE IN EVERYTHING	0
INCL04A	No objective signs of inflammation at Screening, no evident of Sacroiliac joint inflammation or radiographic sacroilitis and hsCRP less than ULN	INCLUDE IN EVERYTHING	0
INCL04B	Total BASDAI < 4 (0–10) at Baseline	INCLUDE IN EVERYTHING	0
INCL05	Subject with no diagnosis of Achilles tendon enthesitis	INCLUDE IN EVERYTHING	0
INCL06	Onset of heel pain < 1 month or > 5 years at baseline	INCLUDE IN EVERYTHING	0
INCL07	Heel enthesitis is not MRI-positive according to the investigator's judgement.	INCLUDE IN EVERYTHING	0
INCL08	Subject is intolerable or toxified or contraindicated to NSAIDs standard treatment for heel enthesitis	INCLUDE IN EVERYTHING	0
INCL09	Rheumatoid factor (RF) or anti-cyclic citrullinated peptide (anti-CCP) antibodies is positive at Screening	INCLUDE IN EVERYTHING	0
INCL10A	Subject are inadequate response to NSAIDs at the highest recommended dose at least 1 month prior to randomization to enroll into study.	INCLUDE IN EVERYTHING	0
INCL10B	Subject is inadequate response or failure to respond, or less than 1 month if therapy	INCLUDE IN EVERYTHING	0
INCL11A	Subject is unstable to remain on regular dose of NSAIDs as part of PsA or axSpA therapy for 2 weeks before study randomization	INCLUDE IN EVERYTHING	0
INCL11B	Subject is unable to remain up to Week 24 on stable regular dose of NSAIDs as part of PsA or axSpA therapy	INCLUDE IN EVERYTHING	0
INCL12A	Patient taking corticosteroid is unable to remain on stable dose of less than or equal of 10 mg/day prednisone for 2 weeks before randomization	INCLUDE IN EVERYTHING	0
INCL12B	Patient taking corticosteroid is unable to remain on stable dose up to week 24	INCLUDE IN EVERYTHING	0
INCL13A	Patient taking MTX or axSpA-sulfasalazine is not taken it for atleast 3 months	INCLUDE IN EVERYTHING	0
INCL13B	Patient taking MTX or axSpA-sulfasalazine is unable to remain on stable dose for at least 4 weeks prior to randomization	INCLUDE IN EVERYTHING	0
INCL13C	Patient taking MTX or axSpA-sulfasalazine is unable	INCLUDE IN	0

Deviation ID	Description of Deviation	Exclusion in Analyses	Severity code
	to remain on stable dose for up to Week 24	EVERYTHING	
INCL14	Patient is on MTX but not on folic acid supplementation at randomization	INCLUDE IN EVERYTHING	0
INCL15A	Patient who is on DMARD other than MTX or - only in case of axSpA - sulfasalazine is not discontinued the DMARD for 4 weeks prior to randomization.	INCLUDE IN EVERYTHING	0
INCL15B	Patients who are on leflunomide, has not been discontinued for 8 weeks unless a cholestyramine washout has been performed prior to randomization to randomized into study.	INCLUDE IN EVERYTHING	0
INCL16	Patients are not TNF $\alpha$ inhibitor-naïve	INCLUDE IN EVERYTHING	0
EXCL01	Chest X-ray or chest MRI with evidence of ongoing infectious or malignant process	INCLUDE IN EVERYTHING	0
EXCL02	Patient took high potency opioid analgesics (e.g. methadone, hydromorphone, morphine).	INCLUDE IN EVERYTHING	0
EXCL03	Previous exposure to secukinumab or other biologic drug directly targeting IL-17 or IL-17 receptor	INCLUDE IN EVERYTHING	0
EXCL04	Patient used any of investigational drug and/or devices within 4 weeks before randomization or a period of 5 half-lives of the investigational drug.	INCLUDE IN EVERYTHING	0
EXCL05A	Patient is using Oral or topical retinoids of psoriasis treatments / medications	INCLUDE IN EVERYTHING	0
EXCL05B	Patient is using Phototherapy of psoriasis treatments / medications and not undergone 4 weeks of washout treatment	INCLUDE IN EVERYTHING	0
EXCL05C	Patient is using Phototherapy of psoriasis treatments / medications and not undergone 2 weeks of washout treatment	INCLUDE IN EVERYTHING	0
EXCL05D	Patient is using Topical skin treatments of psoriasis treatments / medications and not undergone 2 weeks of washout treatment	INCLUDE IN EVERYTHING	0
EXCL06	History of hypersensitivity to any of the study drugs or its excipients or to drugs of similar chemical classes	INCLUDE IN EVERYTHING	0
EXCL07	Any intramuscular or intravenous corticosteroid treatment within 4 weeks before randomization	INCLUDE IN EVERYTHING	0
EXCL08	Any therapy by intra-articular injections (e.g. corticosteroid) within 4 weeks before randomization.	INCLUDE IN EVERYTHING	0
EXCL09	Patients previously have been treated with TNF inhibitors	INCLUDE IN EVERYTHING	0
EXCL10	Patients have received biologic immunomodulating agents	INCLUDE IN EVERYTHING	0
EXCL11	Previous treatment with any cell-depleting therapies including but not limited to anti-CD20, investigational agents	INCLUDE IN EVERYTHING	0
EXCL12	Pregnant or nursing (lactating) women, confirmed by a positive human chorionic gonadotropin (hCG) laboratory test	INCLUDE IN EVERYTHING	0
EXCL13	Women of childbearing potential, defined as all women physiologically capable of becoming pregnant, unless they are using effective methods of contraception before 3 months during dosing of study treatment	INCLUDE IN EVERYTHING	0
EXCL14	Active ongoing inflammatory diseases or including	INCLUDE IN	0

Deviation ID	Description of Deviation	Exclusion in Analyses	Severity code
	inflammatory bowel disease or uveitis.	EVERYTHING	
EXCL15	Patient unacceptable risk for participation in the opinion of the investigator for underlying metabolic, hematologic, renal, hepatic, pulmonary, neurologic, endocrine, cardiac, infectious or gastrointestinal conditions in the opinion of the investigator	INCLUDE IN EVERYTHING	0
EXCL16	Significant medical problems or diseases, including but not limited to the following: uncontrolled hypertension or congestive heart failure or uncontrolled diabetes.	INCLUDE IN EVERYTHING	0
EXCL17A	Any single parameter (AST/SGOT, ALT/SGPT, alkaline phosphatase) exceeded 2 × ULN.	INCLUDE IN EVERYTHING	0
EXCL17B	Total bilirubin concentration is increased above 2 × ULN and serum bilirubin exceeding the value of 1.6 mg/dL (27 µmol/L).	INCLUDE IN EVERYTHING	0
EXCL18	History of renal trauma, glomerulonephritis, or patients with 1 kidney only, or a serum creatinine level exceeding 1.5 mg per dL	INCLUDE IN EVERYTHING	0
EXCL19	Screening total white blood cell (WBC) count less than 3000/µL, or platelets less than 100000/µL or neutrophils less than 1,500/µL or hemoglobin less than 8.5 g per dL (85 g per L).	INCLUDE IN EVERYTHING	0
EXCL20	Active systemic infections during the last 2 weeks (exception: common cold) prior to randomization.	INCLUDE IN EVERYTHING	0
EXCL21	Patient is having history of ongoing, chronic or recurrent infectious disease or evidence of tuberculosis infection	INCLUDE IN EVERYTHING	0
EXCL22	Known infection with human immunodeficiency virus (HIV) or hepatitis B or hepatitis C at screening or randomization	INCLUDE IN EVERYTHING	0
EXCL23	History of lymphoproliferative disease or any known malignancy or history of malignancy of any organ system within the past 5 years.	INCLUDE IN EVERYTHING	0
EXCL24	Current severe progressive or uncontrolled disease which in the judgment of the clinical investigator renders the patient unsuitable for the trial	INCLUDE IN EVERYTHING	0
EXCL25	Inability or unwillingness to undergo repeated venipuncture	INCLUDE IN EVERYTHING	0
EXCL26	Any medical or psychiatric condition which, in the investigator's opinion, would preclude the participant from adhering to the protocol or completing the study per protocol.	INCLUDE IN EVERYTHING	0
EXCL27	Donation or loss of 400 mL or more of blood within 8 weeks before randomization	INCLUDE IN EVERYTHING	0
EXCL28	History or evidence of ongoing alcohol or drug abuse within the last 6 months before randomization.	INCLUDE IN EVERYTHING	0
EXCL29	Plans for administration of live vaccines during the study period or within 6 weeks preceding randomization.	INCLUDE IN EVERYTHING	0
WITH01	Patient becomes pregnant, while taking study medication.	INCLUDE IN EVERYTHING	0
OTH01	Pregnancy test not performed as required per protocol	INCLUDE IN EVERYTHING	0
OTH02	Pregnancy not reported within 24 hrs to Novartis while patient is on study treatment	INCLUDE IN EVERYTHING	0
WITH02	ICF withdrawn but patient continuing in the study	INCLUDE IN EVERYTHING (Delete	0

Deviation ID	Description of Deviation	Exclusion in Analyses	Severity code
		post withdrawal data)	
WITH03	Pregnant patient not withdrawn from study	INCLUDE IN EVERYTHING	0
WITH04	Pregnant patient not withdrawn from study as local workup cannot exclude definite pregnancy	INCLUDE IN EVERYTHING	0
TRT01	Dosing error in comparative dosing phase	INCLUDE IN EVERYTHING	0
OTH03	Rescue medication used	INCLUDE IN EVERYTHING	0
COMD01	Prohibited medication consumed during study or washout period not observed.	INCLUDE IN EVERYTHING	0
EXCL30	Inability or unwillingness to undergo MRI of the feet preceding but enrolled in study	INCLUDE IN EVERYTHING	0
OTH04	Leeds Enthesitis Index assessment is missing but treatment period 1 completed	INCLUDE IN EVERYTHING	0

